8.1.7. Serious Adverse Events and Serious Adverse Device Effects

For recording of a serious adverse event or serious adverse device effect, the study period is defined for each patient as that time period from signature of the ICF to the end of study (ie, patient’s last visit). Serious adverse events or serious adverse device effects occurring in a patient after the end of study for that patient (ie, patient’s last visit) should be reported to the sponsor if the investigator becomes aware of them, following the procedures described in Section 8.1.8.1.

8.1.7.1. Definition of a Serious Adverse Event

A serious adverse event is an adverse event occurring at any dose that results in any of the following outcomes or actions:

- results in death

- is a life-threatening adverse event (ie, the patient was at risk of death at the time of the event); it does not refer to an event which hypothetically might have caused death if it were more severe
- requires inpatient hospitalization or prolongation of existing hospitalization, which means that hospital inpatient admission or prolongation of hospital stay was required for treatment of an adverse event, or that they occurred as a consequence of the event.

Hospitalizations scheduled before the patient signed the ICF will not be considered serious adverse events unless there was worsening of the pre-existing condition during the patient's participation in this study.

- results in persistent or significant disability/incapacity (refers to a substantial disruption of one's ability to conduct normal life functions)
- is a congenital anomaly/birth defect
- an important medical event that may not result in death, be life-threatening, or require hospitalization, but may jeopardize the patient and may require medical intervention to prevent 1 of the outcomes listed in this definition.

Examples of such events are intensive treatment in an emergency room or at home for allergic bronchospasm; blood dyscrasias or convulsions that do not result in hospitalization; or liver injury that meets the criteria for Hy's law; or the development of drug dependency or drug abuse. Note: Any suspected transmission of an infectious agent via a medicinal product is considered an important medical event.

An adverse event that does not meet any of the criteria for seriousness listed above will be regarded as a nonserious adverse event.

8.1.7.2. Definition of a Serious Adverse Device Effect

A serious adverse device effect is an adverse device effect that has resulted in any of the consequences characteristic of a serious adverse event (Section [8.1.7.1](#)).

8.1.7.3. Expectedness

In this study, the reference safety information for determination of expectedness of suspected serious adverse reaction is included in the IB. A serious adverse event that is not included in the relevant reference safety information by its specificity, severity, outcome, or frequency is considered an unexpected adverse event.

The sponsor's Pharmacovigilance Department will determine the expectedness for all serious adverse events.

For the purpose of SUSAR reporting, the version of the IB at the time of occurrence of the SUSAR applies.

8.1.8. Reporting a Serious Adverse Event

8.1.8.1. Investigator Responsibility

To satisfy regulatory requirements, all serious adverse events that occur during the study, regardless of judged relationship to administration of the IMP, must be reported to the sponsor by the investigator. The event must be reported within 24 hours of when the investigator learns about it. Completing the serious adverse event form and reporting the event must not be delayed, even if not all the information is available. The investigator does not need to actively monitor patients for new adverse events once this study has ended.

Serious adverse events occurring after the patient has ended the study should be reported to the sponsor if the investigator becomes aware of them.

The serious adverse event form should be sent to the local safety officer (LSO) or designee (as applicable, for example, a contract research organization [CRO] in a country without a sponsor LSO); the LSO will forward the report to the sponsor's GPSP.

The following information should be provided to record the event accurately and completely:

- study number
- investigator and investigational center identification
- patient number
- onset date and detailed description of adverse event
- investigator's assessment of the relationship of the adverse event to the IMP (no reasonable possibility, reasonable possibility)

Additional information includes:

- age and sex of patient
- date of first dose of IMP
- date and amount of last administered dose of IMP
- action taken
- outcome, if known
- severity
- explanation of assessment of relatedness
- concomitant medication (including doses, routes of administration, and regimens) and treatment of the event
- pertinent laboratory or other diagnostic test data
- medical history
- results of dechallenge/rechallenge, if known
- for an adverse event resulting in death

- cause of death (whether or not the death was related to IMP)
- autopsy findings (if available)

Each report of a serious adverse event will be reviewed and evaluated by the investigator and the sponsor to assess the nature of the event and the relationship of the event to the IMP, study procedures, and to underlying disease.

Additional information (follow-up) about any serious adverse event unavailable at the initial reporting should be forwarded by the investigator within 24 hours of when it becomes known to the same address as the initial report.

For all countries, the sponsor's GPSP will distribute the Council for International Organizations of Medical Sciences (CIOMS) form and/or Extensible Markup Language (XML) file to the LSO/CRO for local submission to the competent authorities, IEC/IRBs, and investigators, according to regulations. For studies in the European Economic Area, submission of SUSARs is done electronically to the EudraVigilance database (via EVWEB or by electronically using the E2B(R3) electronic ICSR form) by the GPSP. The investigator must ensure that the IEC/IRB is also informed of the event, in accordance with national and local regulations.

Blinding will be maintained for all study personnel. Therefore, in case of a SUSAR, only the LSO/CRO unblinded personnel will receive the unblinded report for regulatory submission; the others will receive a blinded report.

8.1.8.2. Sponsor Responsibility

If a serious unexpected adverse event is believed to be related to the IMP (ie, Suspected Unexpected Serious Adverse Drug Reaction, SUSAR), the sponsor will take appropriate steps to notify all investigators participating in sponsored clinical studies of TEV-48574 and the appropriate competent authorities (and IEC/IRB, as appropriate).

In addition to notifying the investigators and competent authorities (and IEC/IRB, as appropriate), other action may be required, including the following:

- modifying the protocol and/or ICF
- discontinuing or suspending the study
- modifying listings of expected toxicities to include adverse events newly identified as related to TEV-48574

8.1.9. Reporting a Serious Adverse Device Effect

The process and contact details for serious adverse device effect reporting are the same as for serious adverse event reporting provided in Section 8.1.8.

Events shall be reported to the IEC/IRB by the investigator and to the regulatory authorities by the sponsor using the appropriate form according to national and local regulations.

The investigator should use [Appendix G](#) to make an initial determination whether the serious adverse event may be related to a device deficiency.

8.1.10. Protocol-Defined Adverse Events of Special Interest

Adverse events of special interest (AESIs)—which are not necessarily adverse drug reactions (ADRs) but are of special interest based on standard drug registration topics, safety findings from previous studies, potential risks associated with biologic immunomodulators, are listed below.

8.1.10.1. Protocol-Defined Adverse Events of Special Interest that Require Reporting to Sponsor's Global Patient Safety and Pharmacovigilance

For purposes of this protocol, the following are considered protocol-defined adverse events of special interest to be sent to the sponsor's GPSP for evaluation:

- systemic severe reactions (including anaphylaxis)
- opportunistic or severe and/or serious infections
- malignancies (including non-melanoma skin cancer)
- liver injury
- severe hematology abnormalities

The process for reporting a protocol-defined adverse event of special interest is the same as that for reporting a serious adverse event (Section 8.1.8). Protocol-defined adverse events of special interest to be reported to GPSP can be either serious or nonserious, according to the criteria outlined in Section 8.1.7.1. Protocol-defined adverse events of special interest that occur before study drug administration and are not serious do not require reporting to GPSP.

Systemic severe reactions (including anaphylaxis)

In the event of suspected anaphylaxis while the patient is at the site, vital signs, including blood pressure, oxygen saturation, and respiration rate, should be measured. Blood samples to test TEV-48574 serum concentration, ADA, and free and total serum TL1A levels should be collected if possible. Collection of blood samples to test tryptase and/or histamine levels are encouraged if available locally at the time of the suspected hypersensitivity event. Other assessments may be performed at the discretion of the investigator. As a precaution, each site should have a resuscitation medication/equipment nearby. If a patient has symptoms of anaphylaxis or severe hypersensitivity, the administration of study drug must be discontinued permanently. In addition, information about all suspected anaphylaxis and hypersensitivity events will be recorded on the Suspected Anaphylaxis CRF, which is based on the 2006 Joint National Institute of Allergy and Infectious Diseases/Food Allergy and Anaphylaxis Network Second Symposium on Anaphylaxis (Sampson et al 2006). These events should be reported to the Sponsor immediately (ie, no more than 24 hours after learning of the event).

Opportunistic or severe and/or serious infections

In the event of opportunistic or severe infections (CTCAE grade 3 to 4), the patient should not receive further study drug until the event has completely resolved. Study drug will be permanently stopped in case of infections following stopping criteria (see Section 4.4.1). Study drug may be restarted following consultation with the Medical Monitor. Treatment of infections should be initiated promptly according to standard of care and all efforts should be made to identify the infectious agent. Events should be reported to the Sponsor immediately (ie, no more

than 24 hours after learning of the event). Examples for opportunistic infections are included in [Appendix J](#).

Malignancies

Any signs or symptoms that could be suggestive of malignancy should be promptly and aggressively evaluated. Patients who develop a malignancy (with the exception of an appropriately treated basal cell carcinoma or squamous cell carcinoma of the skin or in situ carcinoma of uterine cervix) should be withdrawn from study drug and must not receive additional doses of study drug. Malignancies should be reported to the Sponsor immediately (ie, no more than 24 hours after learning of the event).

Liver injury

If any of the following criteria occur, study drug should be withheld and additional monitoring and follow-up assessment will be required (as detailed in the Liver Safety Required Actions and Follow-up Assessments section in [Appendix K](#)):

- ALT or AST ≥ 5 x ULN
- ALT or AST ≥ 3 x ULN with the appearance of fatigue, nausea, vomiting, right upper quadrant pain or tenderness, fever, rash, and/or eosinophilia ($>5\%$)
- AST and/or ALT ≥ 3 fold ULN combined with an elevation of total bilirubin ≥ 2 fold ULN measured in the same blood draw sample or in combination with clinical jaundice or INR >1.5 (not applicable for patients on anticoagulants)

The additional information will be recorded on the Liver Event CRF.

The most appropriate diagnosis or the abnormal laboratory values (if a diagnosis cannot be established) should be recorded on the Adverse Event eCRF (see Section [8.1.3](#)) and reported to the Sponsor immediately (ie, no more than 24 hours after learning of the event).

Severe hematology abnormalities

Predefined confirmed hematology stopping criteria (see Section [4.4.1](#)) should be re-tested every 3 to 5 days until values have returned to above the hematological exclusion criteria threshold, at which point dosing can be resumed (however, two consecutive doses of IMP, should never be given less than 7 days apart).

8.1.10.2. Protocol-Defined Adverse Events of Special Interest that Do Not Require Reporting to Sponsor's Global Patient Safety and Pharmacovigilance

The following are considered protocol-defined adverse events of special interest that do not need to be sent to the sponsor's GPSP department (unless assessed as serious) and will be recorded only in the clinical database:

- administration site reactions (as described in Section [8.2](#))

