3.2. Primary Estimand

The primary estimand in this study is defined by the following attributes:

- **Treatment:** In both UC and CD indications, patients will be randomly assigned to receive any one of the study treatment regimens shown below, in a 1:1:1 ratio:
 - TEV-48574 2250 mg (single loading dose)/900 mg (6 induction doses)
 - TEV-48574 2250 mg (single loading dose)/450 mg (6 induction doses)
 - Matching placebo
- **Target population:** The target population comprises patients with a diagnosis of moderate to severe UC or moderate to severe CD.
- **Variable:** Response for the primary efficacy analysis is defined as clinical remission status at week 14 for UC patients or endoscopic response status at week 14 for CD patients.
- **Handling of intercurrent events:** Intercurrent events addressed here are (a) use of rescue medication; (b) important protocol deviations; (c) UC or CD related surgery; and (d) treatment discontinuation. These intercurrent events will be addressed as follows: (a) Patients who used rescue medications prior to their week 14 evaluation of response (clinical remission in the UC indication or endoscopic response in the CD indication) will be reported as non-responders, ie, the composite variable strategy; (b) Patients experiencing any important protocol deviations, namely, use or changes in other medications, will be analyzed as if the deviation had not occurred, ie, treatment policy strategy; (c) Patients undergoing UC or CD related surgery will be treated as non-responders, ie, the composite strategy; and (d) Patients discontinuing treatment, regardless of the reason, will be treated as non-responders, ie, the composite strategy.
- **Population-level summary:** The population-level summary of interest is the quantity *Posterior Probability* ($p_{d,i} - p_{0,i} > 0$) estimated from a Bayesian Beta-Binomial model for the response rate (clinical remission rate for UC, or endoscopic response rate for CD), $p_{d,i}$, where $i=UC, CD$ and $d=0,1,2$ represent placebo, TEV-48574 low dose (450 mg Q2W), and TEV-48574 high dose (900 mg Q2W), respectively.

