4.4. Stopping Rules for the Study

4.4.1. Individual Stopping Criteria

4.4.1.1. Permanent Individual Withdrawn from IMP

IMP will be discontinued in the event of any of the following:

- The patient develops a serious or severe infection that is:
 - Life threatening

- Requires intensive care unit admission
 - Systemic opportunistic infection including tuberculosis (including pulmonary), cytomegalovirus (CMV; including CMV colitis), and listeriosis
- The patient experiences a serious or severe hypersensitivity reaction following investigational medicinal product (IMP) administration, meeting the Common Terminology Criteria for Adverse Events (CTCAE) criteria 3 to 4:
 - Anaphylaxis
 - Allergic reaction
 - Serum sickness
- The patient experiences a serious or severe Cytokine Release Syndrome following IMP administration, defined as CTCAE grade 3 to 4.
- The patient is diagnosed with malignant neoplasm other than appropriately treated basal cell carcinoma or squamous cell carcinoma of the skin or in situ carcinoma of uterine cervix.
- The patient experiences a serious adverse event where in the investigator, after consultation with the study sponsor's medical expert, assesses there is a reasonable possibility that the serious adverse event may be caused by the IMP.
- The patient becomes pregnant (see Section 8.3).
- The patient requires prohibited medications or an increase from baseline of the medications for the treatment of UC and CD, including surgery for UC and CD (see Section 6.6.3 and Section 6.6.4).
- Neutrophil count of:
 - Absolute neutrophil count $<0.5 \times 10^9/L$ confirmed on repeat testing within 3 to 5 days
 - Absolute neutrophil count $<1.0 \times 10^9/L$ that lasts for 2 weeks (retested every 3 to 5 days) or accompanied by fever $\geq 38.5^\circ\text{C}$
- Lymphocyte count:
 - Lymphocyte count $<0.2 \times 10^9/L$ confirmed on repeat testing within 3 to 5 days
 - Lymphocyte count 0.2 to $0.5 \times 10^9/L$ that lasts for 2 weeks (retested every 3 to 5 days)
- Hemoglobin $<8 \text{ g/dL}$ or an absolute decrease of $\geq 3 \text{ g/dL}$ from baseline (confirmed in repeated test)
- Platelets $<50 \times 10^9/L$ (confirmed in repeated test)
- Liver Chemistry Stopping and Increased monitoring criteria
 - (Refer to Liver Safety Required Actions and Follow up Assessments section in [Appendix K](#))

- alanine aminotransferase (ALT) or aspartate aminotransferase (AST) $\geq 5x$ upper limit of normal (ULN)

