- ALT or AST $\geq 3x$ ULN with the appearance of fatigue, nausea, vomiting, right upper quadrant pain or tenderness, fever, rash, and/or eosinophilia ($>5\%$)
- AST and/or ALT ≥ 3 fold ULN combined with an elevation of total bilirubin ≥ 2 fold ULN measured in the same blood draw sample or in combination with clinical jaundice or in combination of International Normalized Ratio (INR) >1.5 (not applicable for patients on anticoagulants)
- ALT $\geq 3x$ ULN for 4 weeks
- ALT $\geq 3x$ ULN and cannot be monitored weekly for 4 weeks
- QTc >500 msec or change from baseline of QTc >60 msec

4.4.1.2.Temporary Withholding of IMP

IMP will be temporarily discontinued in the event of any of the following:

- Mild or moderate infusion reactions (grade 1 to 2 according to CTCAE of “allergic reaction”) during the infusion. The infusion may be re-initiated, at the discretion of the investigator, at lower speed with or without appropriate premedication, if symptoms are resolved within 1 hour after the stop of infusion/injection. If symptoms return, IMP should be discontinued immediately and permanently.
- A clinically significant infection that the investigator believes may be related to, or exacerbated by, ongoing treatment with the IMP, and none of the permanent stopping rules have been met.
- Absolute neutrophil count $<1.0 \times 10^9/L$
 - Re-testing should be undertaken within 3 to 5 days, and should be re-tested every 3 to 5 days until values have returned to $>1.5 \times 10^9/L$, at which point dosing can be resumed. If the scheduled dose window is missed, re-initiation of study treatment intervention should be restarted as soon as possible but should not result in two consecutive doses being given less than 7 days apart.
- ALT $>3x$ ULN and $<5x$ ULN and bilirubin $<2x$ ULN, without symptoms believed to be related to liver injury or hypersensitivity, and who can be monitored weekly for 4 weeks may continue IMP after discussion with sponsor’s medical expert. If, after 4 weeks of monitoring, ALT $<3x$ ULN and bilirubin $<2x$ ULN, patient will be monitored twice monthly until liver chemistries normalize or return to within baseline. (Refer to Liver Safety Required Actions and Follow up Assessments section in [Appendix K](#)).

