APPENDIX K. LIVER SAFETY: REQUIRED ACTIONS AND FOLLOW-UP ASSESSMENTS GUIDELINES

The liver chemistry stopping and increased monitoring criteria (see Section 4.4.1) have been designed to assure patient safety and evaluate liver event etiology and require follow up assessments as detailed below:

Required Actions and Follow up Assessments	
Actions	Follow up Assessment

 ○ Withhold study drug. ○ Report the event to Sponsor within 24 hours ○ Complete the liver event CRF and complete an SAE/PDAESI form. ○ Perform liver chemistry event follow-up assessments. ○ Monitor the patient and repeat liver chemistries (include ALT, AST, alkaline phosphatase, bilirubin and INR) weekly (if bilirubin >2x ULN or INR>1.5, twice weekly) until liver chemistries resolve, stabilize or return to within baseline ○ Do not restart/patient with study drug unless allowed per protocol and Sponsor approval is granted. ○ If restart is not allowed per protocol or not granted, permanently discontinue study treatment and complete the assessments for the early termination visit and the follow-up period in the study. 	
 ○ Viral hepatitis serology¹ ○ Obtain INR. ○ Obtain blood sample for pharmacokinetic analysis, as soon as possible, and at least within 7 days. ○ Obtain complete blood count with differential to assess eosinophilia. ○ Record the appearance or worsening of clinical symptoms of liver injury, or hypersensitivity, on the AE report form. ○ Record use of concomitant medications on the concomitant medications report form including acetaminophen, herbal remedies, other over the counter medications. ○ Record alcohol use on the liver event CRF ○ If bilirubin and/or INR are elevated: 
 ■ Test Anti-nuclear antibody, anti-smooth muscle antibody, Type 1 anti-live kidney microsomal antibodies, and quantitative total immunoglobulin G (IgG) or gamma globulins. ■ Check serum acetaminophen levels if definite or likely acetaminophen use in the preceding week: ■ Liver imaging (ultrasound, magnetic resonance, or computerized tomography) and/or liver biopsy. ■ Consider a specialist or hepatology consultation.

¹Includes: Hepatitis A immunoglobulin M (IgM) antibody; HBsAg and HBcAb; Hepatitis C RNA; Cytomegalovirus IgM antibody; Epstein-Barr viral capsid antigen IgM antibody (or if unavailable, obtain heterophile antibody or monospot testing); Hepatitis E IgM antibody.

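### Confirmed hematology limits mean permanent withdrawal from IMP in Section 4.4.1.1, but dosing may resume after them in Section 8.1.10.1

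*Protocol*

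**What the plan says.** Section 4.4.1.1 is headed "Permanent Individual Withdrawn from IMP" and opens with "IMP will be discontinued in the event of any of the following". Its hematology entries are neutrophil and lymphocyte counts below a floor, "confirmed on repeat testing within 3 to 5 days"; less extreme counts that persist for 2 weeks (or, for neutrophils, come with fever); hemoglobin below 8 g/dL or a drop of at least 3 g/dL "from baseline (confirmed in repeated test"; and platelets below 50 x 10^9/L, also confirmed.

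Section 4.4.1.2, the temporary list, has one hematology entry: neutrophils below 1.0 x 10^9/L, with dosing resumed above 1.5 x 10^9/L.

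Section 8.1.10.1, under severe hematology abnormalities, points to the confirmed stopping criteria of Section 4.4.1 without separating the two lists. It asks for re-testing every 3 to 5 days "until values have returned to above the hematological exclusion criteria threshold, at which point dosing can be resumed", provided that consecutive doses are never less than 7 days apart. The thresholds it relies on are in exclusion criterion l of Section 5.2.

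For the liver, Section 8.1.10.1 says that study drug is withheld. Appendix K adds "Do not restart/patient with study drug unless allowed per protocol and Sponsor approval is granted", and otherwise requires permanent discontinuation. The ALT item in Section 4.4.1.2 concerns patients "who can be monitored weekly for 4 weeks may continue IMP after discussion", although the list introduces reasons for a temporary stop.

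Section 3.2 sets the outcome rule: "Patients discontinuing treatment, regardless of the reason, will be treated as non-responders".

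**The concern.** A stopping rule has to give one answer for one laboratory result. Here the answer depends on which section the investigator opens. For a confirmed cytopenia, one site stops IMP for good under Section 4.4.1.1, and another re-tests and re-doses under Section 8.1.10.1. Neither has broken the protocol.

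That is first a patient-safety matter. It also affects the data. The number of patients who stopped IMP because of adverse events is a secondary safety endpoint, and it would partly reflect which section a site followed. For a small group of patients the choice could also reach the primary endpoint, because Section 3.2 counts discontinuation of treatment as non-response.

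**Working it through.** **1. The rules side by side** (counts in 10^9/L, hemoglobin in g/dL)

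| Variable | 4.4.1.1, permanent | 4.4.1.2, temporary | Level for resuming under 8.1.10.1 (exclusion criterion l) |
|---|---|---|---|
| Neutrophils | <0.5 confirmed; <1.0 for 2 weeks or with fever | <1.0, resume above 1.5 | 1.5 |
| Lymphocytes | <0.2 confirmed; 0.2 to 0.5 for 2 weeks | not listed | 0.8 |
| Hemoglobin | <8, or drop of 3 or more, confirmed | not listed | 9 |
| Platelets | <50 confirmed | not listed | 100,000/mL as printed |

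**2. Which list does Section 8.1.10.1 mean?** It speaks of confirmed hematology criteria. Lymphocytes, hemoglobin and platelets occur only in the permanent list. The confirmation wording is attached to the hematology entries of that list and not to the neutrophil entry in Section 4.4.1.2. The resumption sentence therefore covers limits that Section 4.4.1.1 makes permanent.

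**3. Hemoglobin.** Take a baseline of 14 g/dL as an example. A confirmed value of 11 gives 14 - 11 = 3, which meets the permanent criterion. Since 11 > 9, the condition for resuming is already met, subject only to the 7-day spacing. In general, a fall of exactly 3 g/dL leaves the value above 9 whenever baseline - 3 > 9, that is, for any baseline above 12 g/dL.

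**4. Platelets.** 100,000/mL x 1,000 mL/L = 10^8/L = 0.1 x 10^9/L. The stopping level is 50 x 10^9/L, and 50 / 0.1 = 500. As printed, the resumption level is 500 times lower than the stopping level, so it is met by values that still require stopping.

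**5. Reach into the primary analysis.** Inputs are 40 patients per arm, Beta(1,1) priors, success at a posterior probability of at least 0.90, and futility below 0.30 at 20 per arm (Sections 10.1, 10.5.4.1 and 10.13, Appendix L). With x responders the posterior for an arm is Beta(1 + x, 41 - x).

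- Check against Table 8: exact binomial enumeration with the futility look gives per-dose success of 90.9% in UC (stated 91%) and 87.0% in CD (stated 87%). The plan's figures reproduce.
- One responder in an arm of 40 is 1/40 = 2.5 percentage points.
- At the decision limit with 3/40 on placebo, 7/40 on active gives Beta(8, 34) against Beta(4, 38), probability 0.903. With 6/40 it is Beta(7, 35), probability 0.844.
- The documents give no frequency for these events. As an assumption, let a share q of active-arm responders be reclassified, so that the active rate p becomes p(1 - q). Without the futility look:

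| q | UC, p = 0.30 v 0.08 | CD, p = 0.34 v 0.12 |
|---|---|---|
| 0 | 91.0% | 87.2% |
| 1% | 90.5% | 86.5% |
| 2.5% | 89.7% | 85.4% |
| 5% | 88.3% | 83.4% |

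**The case against.** The best defence of the text is that sites do not act alone. Section 4.4.1.2 has the investigator inform the sponsor at once, severe hematology abnormalities follow the 24-hour serious-event route, and Section 5.3 asks for discussion before IMP is discontinued. That lowers the chance of divergent handling, but the sponsor would be applying the same two conflicting sentences. The platelet figure may well be a unit slip. If so it still needs correcting, because Section 8.1.10.1 makes it a condition for re-dosing.

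Other objections limit the point, and they stand:

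- **Liver.** A reader might infer that the liver limits are also permanent in one place and re-dosable in another. The text does not support that. Section 8.1.10.1 has no resumption sentence for the liver, and Appendix K allows a restart only where the protocol does and otherwise requires permanent discontinuation. What remains is loose wording between withholding and permanent withdrawal.
- **The ALT item in Section 4.4.1.2.** It sits under the wrong lead-in but agrees with the permanent list, which stops IMP when ALT stays at 3 x ULN or more for 4 weeks or cannot be monitored weekly.
- **Endpoint.** A reader might infer that the conflict reverses a patient's primary outcome. It does so only for someone who would respond at week 14 after re-dosing; all others are non-responders either way. How an interruption with resumed dosing is coded can be left to the SAP, which is not shown.
- **Imbalance.** Nothing in the documents shows that these events will differ between active and placebo. Section 2.2.2.1.2 reports no cytopenias in the first-in-human study.

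**Conclusion.** The hematology contradiction is real and can be verified by reading Sections 4.4.1.1, 4.4.1.2 and 8.1.10.1 together. It affects all four variables and is aggravated by the hemoglobin-drop criterion and the printed platelet unit. It should be fixed because the safety instructions conflict, and not because of any effect on power.

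The statistical consequence is secondary. A single reclassified responder matters at the decision limit (0.903 against 0.844), but that is true of a single reclassified responder from any cause. Over an assumed 1% to 5% of active-arm responders, success falls by 0.5 to 2.7 points in UC (91.0 - 90.5; 91.0 - 88.3) and by 0.7 to 3.8 points in CD (87.2 - 86.5; 87.2 - 83.4). The true share is unknown. A reader might infer that the sample size or Table 8 is wrong; neither is, and the per-dose success figures reproduce. No view is taken on which dosing rule is right.

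**What to change.** Reconcile Sections 4.4.1.1, 4.4.1.2, 5.2 (criterion l) and 8.1.10.1 so that each hematology limit has one consequence, permanent or temporary, in identical words wherever it appears. Settle in the same step how the hemoglobin-drop criterion relates to the level for resuming, and check the platelet unit. The choice of rule belongs to the sponsor's medical and safety staff.

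Two lesser wording changes can go with it: align the withholding language of Section 8.1.10.1 and the restart clause of Appendix K with the liver limits listed as permanent in Section 4.4.1.1, and move the ALT item in Section 4.4.1.2 out from under the lead-in on temporary stopping.

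The cost is a safety-text clarification to sites or a short amendment. Sample size, primary model and decision cutoffs do not change. Once the rule is settled, a blinded look at patients already handled under either section would show whether the conflict has had any effect.
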